4.8.3.3 Secondary Efficacy Analyses

The incidence of RSV hospitalization during 5 months of the RSV season will be summarized by treatment group. The same methods described above for the primary efficacy endpoint will be used to assess treatment effect on RSV hospitalization. Following a hierarchical testing procedure, the secondary efficacy endpoint will be tested at the significance level of 2-sided 0.05 if the primary analysis on the primary efficacy endpoint has achieved statistical significance at the level of 2-sided 0.05.

4.8.4 Safety Analysis

Safety of MEDI8897 will primarily be assessed by the occurrence of treatment-emergent AEs and SAEs. Adverse events will be graded according to the current version of the NCI CTCAE where applicable for pediatric assessments. Adverse events will be coded by

Medical Dictionary for Regulatory Activities (MedDRA) and the type, incidence, severity and relationship to study investigational product will be summarized by treatment group. Other safety assessments will include:

- Occurrence of AESIs to include targeted AEs of hypersensitivity (including anaphylaxis), thrombocytopenia, and immune complex disease (eg, vasculitis, endocarditis, neuritis, and glomerulonephritis) following investigational product administration.
- Occurrence of NOCDs following investigational product administration.

4.8.5 Analysis of Pharmacokinetics and Anti-drug Antibody

4.8.5.1 Analysis of Pharmacokinetics

Following a single dose of MEDI8897, individual MEDI8897 serum concentration data will be tabulated by treatment group along with descriptive statistics. Terminal-phase half-life ($t_{1/2}$) will be estimated using non-compartmental analysis, if data permit.

4.8.5.2 Analysis of Anti-drug Antibodies

The incidence of ADA to MEDI8897 will be assessed and summarized by number and percentage of subjects that are ADA positive by treatment group. The ADA titer will be listed by subject at different time points. The impact of ADA on PK, and association with TEAEs and TESAEs will be assessed.

4.8.6 Exploratory Analyses

The magnitude of HRU (eg, number of admissions to hospitals and ICUs and duration of stay; number of subjects who require respiratory support and supplemental oxygen and the duration of use; number and types of outpatient visits, eg, ER, urgent care, outpatient clinic; and number of prescription and OTC medications and duration of use) will be summarized overall by treatment group, and for the following subgroups: subjects with at least one medically attended LRTI caused by RT-PCR confirmed RSV, subjects with medically attended LRTI not caused by RSV, and subjects without medically attended LRTI.

Caregiver burden (eg, caregiver missed work days, subject absence from day care) for subjects with medically attended LRTI caused by RT-PCR-confirmed RSV will be summarized by treatment group.

4.8.7 Data Monitoring Committee

An independent DMC will review safety data regularly and make recommendations regarding further study conduct.

5 ASSESSMENT OF SAFETY

5.1 Definition of Adverse Events

The ICH Guideline for Good Clinical Practice E6 (R1) defines an AE as:

Any untoward medical occurrence in a patient or clinical investigation subject administered a pharmaceutical product and which does not necessarily have a causal relationship with this treatment. An AE can therefore be any unfavorable and unintended sign (including an abnormal laboratory finding), symptom, or disease temporally associated with the use of a medicinal product, whether or not considered related to the medicinal product.

An AE includes but is not limited to any clinically significant worsening of a subject's pre-existing condition. An abnormal laboratory finding (including electrocardiogram [ECG] finding) that requires medical intervention by the investigator, or a finding judged by the investigator as medically significant should be reported as an AE. If clinical sequelae are associated with a laboratory abnormality, the diagnosis or medical condition should be reported (eg, renal failure, hematuria) not the laboratory abnormality (eg, elevated creatinine, urine red blood cells [RBC] increased). Abnormal laboratory values that are not, in the investigator's opinion, medically significant and do not require intervention should not be reported as AEs.

Adverse events may be treatment emergent (ie, occurring after initial receipt of investigational product) or nontreatment emergent. A nontreatment-emergent AE is any new sign or symptom, disease, or other untoward medical event that begins after written informed consent has been obtained but before the subject has received investigational product.

Elective treatment or surgery or preplanned treatment or surgery (that was scheduled prior to the subject being enrolled into the study) for a documented pre-existing condition that did not worsen from baseline is not considered an AE (serious or nonserious). An untoward medical event occurring during the prescheduled elective procedure or routinely scheduled treatment should be recorded as an AE or SAE.

5.2 Definition of Serious Adverse Events

A SAE is any AE that:

- Results in death
- Is immediately life-threatening

- Requires inpatient hospitalization or prolongation of existing hospitalization
- Results in persistent or significant disability/incapacity
- Is a congenital anomaly/birth defect in offspring of the subject
- Is an important medical event that may jeopardize the subject or may require medical intervention to prevent one of the outcomes listed above

Medical or scientific judgment should be exercised in deciding whether expedited reporting is appropriate in this situation. Examples of medically important events are intensive treatment in an emergency room or at home for allergic bronchospasm, blood dyscrasias, or convulsions that do not result in hospitalizations; or development of drug dependency or drug abuse.

5.3 Definition of Adverse Events of Special Interest

An AESI is one of scientific and medical interest specific to understanding of the investigational product and may require close monitoring and rapid communication by the investigator to the sponsor. An AESI may be serious or non-serious. The rapid reporting of AESIs allows ongoing surveillance of these events in order to characterize and understand them in association with the use of this investigational product.

5.3.1 Hypersensitivity, Including Anaphylaxis

Administration of polyclonal immunoglobulin preparations and mAbs has been associated with hypersensitivity (including anaphylaxis) that occurs during or after dosing. A hypersensitivity reaction is defined as an acute onset of an illness with involvement of the skin, mucosal tissue, or both during administration of investigational product (but does not meet the definition of anaphylaxis). Anaphylaxis is a rare event, usually occurring after subsequent exposure to antigen, and it is most commonly accompanied by severe systemic skin and or mucosal reactions. It is potentially a fatal, systemic allergic reaction that is distinct from simple allergic reactions (eg, rash, pruritus) because of the simultaneous involvement of several organ systems ([Sampson et al, 2006](#)). A full definition of anaphylaxis is provided in [Appendix 3](#). See Section 5.5 for recording AEs.

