4.3 Description of Study Procedures

4.3.1 Efficacy

4.3.1.1 Lower Respiratory Tract Infection

Subjects will be monitored throughout the study for LRTI. All subjects seeking medical attention for a respiratory illness (defined as new onset events indicating a change from the child's baseline medical status referable to the lower respiratory tract) will be evaluated for the occurrence of LRTI (Table 4.3.1.1-1). These events may occur in the inpatient or outpatient setting. Subjects who have a primary hospitalization for a respiratory illness, or who have a respiratory deterioration during a hospitalization, or who seek outpatient medical attention, including ER visits, for a respiratory illness will be assessed for RSV by diagnostic testing of respiratory secretions. Testing for RSV will be performed centrally using the FDA-approved and CE-marked in vitro diagnostic real-time RT-PCR assay (Lyra RSV + hMPV Assay, Quidel, San Diego, CA www.quidel.com). A diagnosis of RSV LRTI requires having a respiratory sample positive for RSV by RT-PCR.

To meet the protocol-specified criteria for LRTI, subjects with signs of LRTI must have documented physical exam findings of rhonchi, rales, crackles, or wheeze AND any of the following:

- Increased respiratory rate at rest (age: < 2 months, ≥ 60 breaths/min; 2–6 months, ≥ 50 breaths/min; > 6 months – 2 years, ≥ 40 breaths/min), OR
- Hypoxemia (in room air - oxygen saturation < 95% at altitudes ≤ 1800 meters or < 92% at altitudes > 1800 meters), OR
- Clinical signs of severe respiratory disease (eg, acute hypoxic or ventilatory failure, new onset apnea, nasal flaring, intercostal, subcostal or supraclavicular retractions, grunting) or dehydration secondary to inadequate oral intake due to respiratory distress (need for intravenous fluid).

Table 4.3.1.1-1 Elements to Evaluate for Case Definition of RSV LRTI

Specificity	Sensitivity	Medical Significance
RSV Confirmed: 
 Positive RT-PCR 	Documented PE findings localizing to lower respiratory tract: 
 Rhonchi Rales Crackles Wheeze 	Objective measures of clinical severity: 
 Increased respiratory rate Hypoxemia Acute hypoxic or ventilatory failure New onset apnea Nasal flaring Retractions Grunting Dehydration Prescription medications (only for children with underlying lung disease)

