5.5 Recording of Adverse Events

Adverse events, including SAEs, AESIs and NOCDs, will be recorded on the eCRF using a recognized medical term or diagnosis that accurately reflects the event. These events will be assessed by the investigator for severity, relationship to the investigational product and study procedure(s), possible etiologies, and whether the event meets criteria of an SAE (see Section 5.2 and 5.6), or is an AESI or NOCD (see Section 5.3, 5.4 and 5.7) and therefore requires immediate notification to the sponsor. See Appendix 2 for guidelines for assessment of AE severity and relationship to IP. If an AE evolves into a condition that meets the definition of “serious,” it will be reported on the AE form in the eCRF as a serious adverse event.

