5.5.1 Time Period for Collection of Adverse Events

Adverse events and SAEs will be collected from the time of signature of informed consent through the follow-up period (Day 361 visit).

All AESIs and NOCDs will be collected from the time of dosing through the follow-up period (Day 361 visit).

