5.7.2 Adverse Events of Special Interest

5.7.2.1 Hypersensitivity, Including Anaphylaxis

Events of hypersensitivity, including anaphylaxis (as defined in [Appendix 3](#)), require that the investigator or other site personnel inform appropriate sponsor study representatives immediately, or **no later than 24 hours** of when he or she becomes aware of the event. The designated sponsor study representative works with the Investigator to ensure that all relevant information is provided and entered in EDC. If the event is considered serious it must be reported as an SAE (see Section [5.6](#)).

Signs of hypersensitivity include urticaria, pruritis, angioedema, skin rash, difficulty breathing, and wheezing. Parent(s)/legal representatives will be provided a card with this information to aid in prompt identification and reporting of these signs. Parent(s)/legal representatives will be instructed to immediately report the occurrence of any of these findings to the site investigator who should then report the events to appropriate sponsor study representatives immediately, or **no later than 24 hours** of when he or she becomes aware of the event.

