3.7.6 Other Safety Evaluations

TEAEs, AESIs, skin reactions, and skin hypersensitivity reactions will also be summarized by timing relative to dosing ('within 1 day/greater than 1 day,' 'within 7 days/greater than 7 days').

Additional data collected throughout the study include screen failure data, significant findings in medical history and physical exam, vital signs, and concomitant medications through Day 361. Data listings will be provided and no formal analyses will be conducted on these data. Upon review of the listings, additional summary tables may be generated as appropriate.

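### The protocol's definition of a non-anaphylactic hypersensitivity reaction admits only onset during the injection, contradicting its own paragraph and the SAP timing tables, and the separate list of reportable signs overlaps with RSV illness

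*Protocol*

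**What the plan says.** AESI occurrence is part of the second secondary endpoint (Protocol 2.2.2). Under Protocol 5.5 the investigator records a diagnosis, considers causes, and decides whether the event is serious "or is an AESI or NOCD (see Section 5.3, 5.4 and 5.7) and therefore requires immediate notification to the sponsor". The AESI decision is thus referred to both 5.3 and 5.7.

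- **Protocol 5.3.1, opening sentence.** It associates this class of product with "hypersensitivity (including anaphylaxis) that occurs during or after dosing".
- **Protocol 5.3.1, next sentence.** It defines a reaction that falls short of anaphylaxis as an "acute onset of an illness with involvement of the skin, mucosal tissue, or both during administration of investigational product".
- **Protocol 5.7.2.1.** "Signs of hypersensitivity include urticaria, pruritis, angioedema, skin rash, difficulty breathing, and wheezing". Parents are "instructed to immediately report the occurrence of any of these findings to the site investigator who should then report the events to appropriate sponsor" representatives, within 24 hours at most. The section refers to Appendix 3 for anaphylaxis but not to 5.3.1.
- **Protocol 5.5.1.** AESIs are collected from dosing to the Day 361 visit.
- **Protocol 4.3.1.1.** An LRTI needs "documented physical exam findings of rhonchi, rales, crackles, or wheeze" plus a measure of severity.
- **SAP v5 3.7.2.** AESIs are summarized by arm, system organ class and preferred term. There is no case definition or term list for hypersensitivity.
- **SAP v5 3.7.6.** "TEAEs, AESIs, skin reactions, and skin hypersensitivity reactions will also be summarized" by timing from dosing, split at 1 day and again at 7 days.

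**The concern.** The only stated definition of a non-anaphylactic reaction excludes any onset after the needle is withdrawn. A site that follows it would leave urticaria a few hours after dosing out of the AESI record, while a site guided by the opening sentence or by 5.7.2.1 would include it. The AESI count would then depend partly on which sentence each site used.

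The second issue is overlap with efficacy. Wheezing and difficulty breathing are common ground between the 5.7.2.1 list and the LRTI endpoint. If a site used the list as a case definition, some RSV illness would be recorded as hypersensitivity. The drug is meant to reduce RSV illness, so this misclassification would fall more heavily on placebo and could offset a true excess on MEDI8897.

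**Working it through.** **Two cases followed through the text**

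| Place | Urticaria 6 hours after dosing, no other organ | Wheeze during an RSV illness on Day 60 |
|---|---|---|
| Protocol 5.3.1, definition | Not an AESI: onset too late | Not an AESI: no skin or mucosal sign, onset too late |
| Protocol 5.3.1, opening sentence | Timing within scope | Timing within scope |
| Protocol 5.7.2.1 | Listed sign, to be reported | Listed sign, to be reported |
| Protocol 5.5 | Investigator decides | Investigator decides after weighing cause |
| Protocol 5.5.1 | Inside the collection period | Inside the collection period |
| SAP v5 3.7.2 | No rule to include or exclude | No rule to include or exclude |
| SAP v5 3.7.1 and 3.7.3 | In the TEAE and skin-reaction tables | In the TEAE table under its diagnosis |
| SAP v5 3.7.6 | Has a row (within 1 day) if flagged | Has rows (beyond 1 and 7 days) if flagged |

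The definition stands alone against the other timing provisions. Vital signs at 30 and 60 minutes after dosing (4.5.1.3) and the parents' card (5.7.2.1) also suggest that later reactions were meant to be caught.

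**Direction of any RSV misclassification**

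The plan gives no figure for hypersensitivity. The only usable inputs are the design rates in Protocol 4.8.2: 8% RSV LRTI on placebo and a 70% relative reduction, with 1,000 and 500 infants. They reproduce the stated power of about 99% (99.6% by a two-proportion test, 99.8% by a Wald test on the log relative risk).

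- Placebo: 500 × 0.08 = 40 RSV LRTIs.
- MEDI8897: 0.08 × (1 − 0.70) = 0.024; 1,000 × 0.024 = 24 RSV LRTIs.

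Let f be the share of these recorded as hypersensitivity. f is **not in the documents**; I assume it is the same in both blinded arms.

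- Ratio of misclassified rates: 0.024f / 0.08f = 0.30 for any f above zero.
- Difference: (0.08 − 0.024) × f = 0.056f, higher on placebo. A true drug-caused rate equal to 0.056f would be cancelled.

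| Assumed f | MEDI8897 events | Placebo events | True rate cancelled |
|---|---|---|---|
| 0 | 0 | 0 | none |
| 5% | 1.2 | 2.0 | 0.28% |
| 10% | 2.4 | 4.0 | 0.56% |
| 100% (ceiling) | 24 | 40 | 5.6% |

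**What the literal definition could remove from the AESI table**

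Assume, again without a source in the documents, a true non-anaphylactic reaction rate of 0.5% and a share s of reactions that begin during the injection. All reactions: 1,000 × 0.005 = 5 expected, and the chance of at least one is 1 − 0.995^1000 = 99.3%. With s from 1% to 10%, the expected AESI count is 5s = 0.05 to 0.5, and the chance of at least one is 1 − (1 − 0.005s)^1000 = 4.9% to 39%. This concerns the AESI table only; the other tables would still hold all five.

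**The case against.** The case against reading much into this is strong.

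- Section 5.7.2.1 is a notification rule with a sign list for parents. It does not say that wheeze alone is a case. Under 5.5 the investigator records a diagnosis and considers causes, so an RSV illness should be entered as such.
- Anaphylaxis, part of the same AESI, has its own criteria in Appendix 3, with onset within minutes to hours. Thrombocytopenia and immune complex disease are untouched by 5.3.1.
- SAP v5 3.7.3 compares skin reactions, and those identified as allergic, between arms with no limit on onset, and 3.7.6 splits them by timing. Late respiratory terms would show in the AESI tables by preferred term.
- The suspension item on hypersensitivity in Protocol 4.4 (item 3) turns on graded AEs judged related, not on the AESI flag. Appendix 2 makes an event unrelated if the disease is clearly the likelier explanation.
- In the earlier infant study (Protocol 1.4), bronchiolitis was reported in 7/71 MEDI8897 infants and 5.6% of placebo infants, with no AESIs.

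Nearly all of this stands, and it limits the consequence. The last item carries little weight: it is a 30-day interim from 89 infants, and that study's AESI definition is not given. None of it removes the contradiction in 5.3.1 or supplies the case definition missing from the SAP.

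**Conclusion.** The contradiction in Protocol 5.3.1 is established from the text. Applied as written, it excludes post-injection, non-anaphylactic reactions from one component of a secondary safety endpoint. They remain visible in the TEAE and skin-reaction tables. The overlap between 5.7.2.1 and the LRTI signs is a risk, not a demonstrated bias. Its direction (more on placebo) follows from the design rates if f is equal in both arms; its size is unknown because f is unknown. The tables above are conditional illustrations, not estimates.

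A reader might go further in four ways that the documents do not support.

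- *The endpoint must be either almost empty or contaminated.* Investigator judgement, Appendix 3 and the SAP tables lie between these extremes.
- *A placebo excess of stated size can be expected.* No document gives the share of RSV illness that would be misrecorded.
- *The 4.4 suspension criterion is distorted.* It does not use the AESI flag.
- *The 1-day and 7-day splits could serve as cut-offs for all AESIs.* Protocol 5.3.2 puts typical serum sickness onset at 1 to 2 weeks, so a 7-day limit would drop much of another named AESI.

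The point is worth correcting because it is cheap; it does not threaten the trial's main conclusions.

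**What to change.** 1. In Protocol 5.3.1, reconcile the definition with the section's opening sentence, so that onset during or after administration counts.
2. In Protocol 5.7.2.1, state that the listed signs prompt notification and assessment and do not by themselves define the AESI. Add a reference to 5.3.1, as 5.7.2.2 already has to 5.3.2.
3. In SAP 3.7.2, derive the hypersensitivity AESI flag under blind from onset date and preferred term, with the term list set by the clinical team. Fix the algorithm before the primary analysis: sponsor staff are unblinded then (Protocol 4.6.3.2), while AESIs are collected to Day 361.
4. Keep the SAP 3.7.6 timing splits for presentation. Do not apply them as windows to immune complex disease or thrombocytopenia.
5. Check item 3 of Protocol 4.4 for consistency with the reconciled definition. No stopping or clinical rule is proposed here.

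The cost is protocol and eCRF-guidance wording plus one derived variable, with no new data. The downside is that some more post-dose skin events will count as AESIs.

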5.3.2 Immune Complex Disease

Immune complex disease can manifest in the form of a number of conditions such as vasculitis, endocarditis, neuritis, glomerulonephritis, serum sickness, and arthralgias. Drug-induced immune complex (type III) hypersensitivity reactions can occur when host immune system generates antibodies to drug resulting in soluble circulating antigen-antibody complexes formation and their deposition in blood vessels. Subsequently this initiates tissue

damaging inflammatory reactions mediated by complement and/or leukocytes and mast cells. The pathology and clinical manifestations are dependent on the tissues/organs involved, with vascular, skin and renal tissues being common sites of injury. Common examples of immune complex hypersensitivity reactions are serum sickness (systemic) and Arthus reactions (local). The clinical manifestations of serum sickness include skin rash, fever, malaise and polyarthralgias or polyarthritis. Symptoms typically develop 1 to 2 weeks after first exposure to antigen and usually resolve in several weeks after withdrawal of the causative agent. Serum sickness needs to be differentiated from other ‘serum-sickness-like’ reactions that have a similar clinical presentation (eg, viral infections, anti-seizure drugs), but are believed to have different pathogenic mechanisms. Both serum sickness and serum sickness-like reactions have been reported with mAbs (eg, rituximab, infliximab). Clinical presentation and time to onset should be taken into account for the diagnosis and differentiation of these reactions. Diagnosis of these suspected reactions is best confirmed via biopsy of the affected tissues. See Section 5.5 for recording AEs.

5.3.3 Thrombocytopenia

Thrombocytopenia is a disorder in which there is an abnormally low platelet count; a normal platelet count ranges from 150,000 to 450,000 platelets per μL . The 3 major causes of low platelet counts include: 1) insufficient platelet synthesis in the bone marrow; 2) increased breakdown of platelets in the bloodstream; and 3) increased breakdown of platelets in the spleen or liver. General symptoms of thrombocytopenia include bleeding in the mouth and gums, bruising, nosebleeds, and petechiae (pinpoint red spots/rash). Severe bleeding is the major complication, which may occur in the brain or gastrointestinal tract. Drug-induced thrombocytopenia is a reversible form of thrombocytopenia that should be suspected in a subject who presents with new onset thrombocytopenia or recurrent episodes of acute thrombocytopenia, without an obvious alternative etiology. It is commonly induced by drug-dependent antibodies that cause platelet destruction or clearance by the reticuloendothelial system (drug-induced immune thrombocytopenia), and less commonly by drug-induced bone marrow suppression or autoimmune thrombocytopenia that is initiated by exposure to the offending drug but persists in its absence. The initial approach to the subject with suspected drug-induced thrombocytopenia involves confirming thrombocytopenia, establishing a temporal relationship to a drug, and eliminating other causes of thrombocytopenia. The diagnosis is made clinically by documenting prompt resolution of thrombocytopenia after discontinuation of the suspected drug (typically within 1 week). Most subjects with drug-induced thrombocytopenia require no specific treatment, as their platelet counts will recover promptly following withdrawal of the causative agent. See Section 5.5 for recording AEs.

